7.4 PRIMARY ENDPOINT(S)

7.4.1 Primary analysis of the primary endpoint(s)

The primary analysis will be performed on the FAS (OC). The primary analysis is an REML-based MMRM approach comparing the change from baseline in HbA1c after 52 weeks of treatment. All randomised treatment groups will be included in the same analysis.

The primary analysis model will be: HbA1c change from baseline at each on-treatment visit = baseline HbA1c + age + baseline renal function + sex + visit by treatment interaction + random error,

where 'baseline renal function', 'sex' and 'visit by treatment interaction' are fixed classification effects, and 'baseline HbA1c' and 'age' are linear covariates.

In all modelling, the variable 'baseline renal function' will be defined as last eGFR value before first intake of study treatment categorised according to the CKD staging. Note that baseline renal function refers to the eGFR categorization (≥ 60 mL/min/1.73 m 2 , < 60 mL/min/1.73 m 2). Such categorization is applicable to the analysis of other endpoints as well.

For each patient, the error terms from all the visits represent the within-patient variability, and are assumed to follow a multivariate normal distribution with an unstructured covariance matrix. If an unstructured (co)variance structure fails to converge, the following structures will be tested: compound symmetry, variance components and Toeplitz. The (co)variance structure converging to the best fit, as determined by Akaike's information criterion, will be used. This rule will also be used for other MMRM analyses unless otherwise stated.

The treatment effect will be estimated on the basis of the least square mean treatment difference at week 52 extracted from the primary analysis model.

The Kenward-Roger approximation will be used to estimate the denominator degrees of freedom. Significance tests will be based on least-squares means using a two-sided $\alpha = 0.05$ (two-sided 95% confidence intervals).

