7.2.2 Primary endpoint analyses

For primary endpoint, refer to Section [2.1.2](#). The primary analysis will be performed on the FAS with treatment assignment as randomised.

The primary analysis is a restricted maximum likelihood (REML)-based mixed model repeated measures (MMRM) comparing the change in HbA1c (in units of %) from baseline after 52 weeks of double-blind treatment.

The statistical model will include fixed classification effects for treatment, gender, baseline renal function, visit and visit-by-treatment interaction, and a linear covariate for baseline HbA1c and age. An unstructured covariance structure will be used to model the within-patient errors. If this unstructured covariance structure fails to converge, the following structures will be tested: compound symmetry, variance components and Toeplitz. The covariance structure converging to the best fit, as determined by Akaike's information criterion, will be used.

The Kenward-Roger approximation will be used to estimate the denominator degrees of freedom.

Only the available data that were observed while patients were on treatment will be included in the analysis. Missing data are handled implicitly by the above statistical model, rather than using any imputation. This approach, referred to as observed case (OC), will additionally set all values measured after rescue medication taken to missing.

Sensitivity analyses of the primary endpoint will be performed. Such sensitivity analyses will be specified in the TSAP.

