7.5 DETERMINATION OF SAMPLE SIZE

Based upon previous experiences with these compounds, the difference in HbA1c change from baseline after 52 weeks between the treatment groups can be assumed to be 0.5% with a standard deviation of 0.85%. With a randomisation ratio of 1:1, it is assumed that the sample size of each group (empagliflozin 10 mg and placebo) is 62 patients. Assuming that approximately 3% of patients will not be eligible for inclusion into FAS due to the absence of a post-baseline primary endpoint value, 64 patients for the empagliflozin 10 mg group and 64 patients for the placebo group need to be randomised. With this sample size, a power of 90% for a two-sided test at level $\alpha=5\%$ for the primary endpoint will be achieved.

Calculations were performed using nQuery Advisor® 6.1 statistical package by [REDACTED]
[REDACTED].

8. INFORMED CONSENT, TRIAL RECORDS, DATA PROTECTION, PUBLICATION POLICY, AND ADMINISTRATIVE STRUCTURE

The trial will be carried out in compliance with the protocol, the ethical principles laid down in the Declaration of Helsinki, in accordance with the ICH Harmonised Guideline for GCP, relevant BI Standard Operating Procedures (SOPs), the Japanese GCP regulations (Ministry of Health and Welfare Ordinance No. 28, March 27, 1997), Good Post-Marketing Study Practice (GPSP), Good Vigilance Practice (GVP) and other relevant regulations. Investigators and site staff must adhere to these principles. Deviation from the protocol, the principles of ICH GCP or applicable regulations will be treated as “protocol deviation”.

Standard medical care (prophylactic, diagnostic and therapeutic procedures) remains the responsibility of the treating physician of the patient.

The investigator will inform the sponsor immediately of any urgent safety measures taken to protect the trial patients against any immediate hazard, as well as of any serious breaches of the protocol, of ICH GCP, or of Japanese GCP.

The Boehringer Ingelheim transparency and publication policy can be found on the following web page: trials.boehringer-ingelheim.com. The rights of the investigator and of the sponsor with regard to publication of the results of this trial are described in the investigator contract. As a rule, no trial results should be published prior to finalisation of the clinical trial report.

The certificate of insurance cover is made available to the investigator and the patients, and is stored in the ISF.

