4. CHANGES IN THE PLANNED ANALYSIS OF THE STUDY

Descriptions in the CTP related to statistical analysis will be changed as follows:

- [REDACTED]
- [REDACTED]
- [REDACTED]
- Descriptive statistics on the impact of COVID-19 on study visits as well as trial medication intake will be provided if any.
- The definition of iPDs will be specified in the DV domain instead of the TSAP prior to DBL.

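### Optional precision gain: the primary MMRM uses one baseline-HbA1c slope for all visits, which can cost some Week 52 precision if that slope grows over time

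*SAP*

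**What the plan says.** SAP 7.4.1 writes the right-hand side of the primary model as "baseline HbA1c + age + baseline renal function + sex + visit by treatment interaction + random error". Baseline HbA1c and age enter as linear covariates, and the only term that varies by visit is the treatment effect. Protocol 7.2.2 agrees: it has visit, treatment and their interaction, plus "a linear covariate for baseline HbA1c and age". The synopsis gives the same structure. The within-patient covariance is unstructured.

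The primary result is the "least square mean treatment difference at week 52 extracted from the primary analysis model", tested two-sided at 5%.

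No readable section lets the baseline slope differ by visit, either in the primary model or in a sensitivity analysis. The secondary endpoints (SAP 7.8.5) use a Week 52 ANCOVA, so their baseline slope is specific to Week 52.

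For the sample size, protocol 7.5 says the difference "can be assumed to be 0.5% with a standard deviation of 0.85" percentage points. It does not say whether that SD is before or after covariate adjustment.

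**The concern.** A single slope assumes that change from baseline depends on baseline HbA1c equally strongly at Week 4 and at Week 52. HbA1c responds slowly, so a weaker relation at Week 4 is plausible. SAP 6.7 itself warns that the first visit window, which opens on day 2, may understate the effect for parameters that react slowly. It does not name HbA1c or baseline slopes, so this is support and not proof.

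The likelihood gives most weight to visits with small residual variance. If the early visits have both a shallow slope and a small variance, the shared slope settles near the early value. Variation at Week 52 that baseline could explain then stays in the residual, and the standard error of the primary comparison is larger than the same data allow. Precision is at stake here; validity is not.

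**Working it through.** **Inputs from the documents.** Difference 0.5, SD 0.85, 62 evaluable per arm, 1:1 allocation, two-sided 5% (protocol 7.5, SAP 7.4.1); five on-treatment HbA1c visits (SAP Table 6.7:2).

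**Inputs assumed.** Baseline SD, slope at each visit, residual SD at each visit and inter-visit correlation. None is in the documents, so ranges are used.

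**Step 1: the plan's own figure.** SE = 0.85 × √(2/62) = 0.1527. A two-sample t-test then has 90.1% power (89.7% with 61 per arm), and 62/0.97 = 63.9, rounded up to 64. The stated sample size reproduces.

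**Step 2: formula.** Let b be the vector of true visit slopes, V the baseline variance, Σ the residual covariance, s the Week 52 residual SD and c the shared slope. In large samples with unstructured covariance, c minimises log det[Σ + V(b − c)(b − c)′]. Then:

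- planned model: SE = √{(2/62) × [s² + V(b₅₂ − c)²]}
- with baseline by visit: SE = √(2/62) × s

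**Step 3: one case in full.** Baseline SD 0.75 (V = 0.5625), slopes from −0.10 to −0.45, raw Week 52 SD 0.85.

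- s² = 0.7225 − 0.5625 × 0.45² = 0.6086, so the by-visit SE is √(0.6086 × 2/62) = 0.1401.
- Residual SD rising from 0.4 to 1.0 of its Week 52 value: c lies between −0.11 and −0.02, depending on the correlation.
  - At c = −0.11 the bracket is 0.6086 + 0.5625 × 0.34² = 0.6736. The SE is 0.1474, which is 5.2% larger, and (0.34/0.45)² = 57% of the baseline adjustment is lost.
  - At c = −0.02 the bracket is 0.6086 + 0.5625 × 0.43² = 0.7126. The SE is 0.1516, which is 8.2% larger, and (0.43/0.45)² = 91% is lost.
- Flat residual SD: c is between −0.31 and −0.29. The bracket is 0.6196 to 0.6230, and the SE is 0.1414 to 0.1418, about 1% larger.

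**Step 4: grid.** Baseline SD 0.6 and 0.75; slopes equal at −0.30, or −0.05 to −0.35, −0.10 to −0.40, −0.10 to −0.45; residual SD steeply rising, moderately rising or flat; correlation compound symmetric 0.5 and 0.7, or AR(1) 0.7 and 0.85.

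- The Week 52 SE is 0% to 8.3% larger and the power loss is 0 to about 4 points.
- When slopes grow, the share of the Week 52 adjustment lost is 10–17% with flat residual SD, and from 51% to all of it with the steepest rise.

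**Step 5: simulation.** 4,000 trials per setting, complete data, correlation 0.5, allocation stratified at an assumed cut 0.6 SD above the baseline mean. Excess SE of the planned model at Week 52:

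| Baseline SD; slopes | Residual SD 0.4→1.0 | 0.6→1.0 | Flat |
|---|---|---|---|
| 0.75; −0.10 to −0.45 | 5.8% | 3.7% | 0.7% |
| 0.6; −0.05 to −0.35 | 2.5% | 1.6% | 0.2% |

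In the first row, first column, the SE is 0.1479 against 0.1398 and power is 92.3% against 94.1%. With equal slopes the added term makes the SE 0.1% to 0.2% larger. Estimates average about −0.50 under both models, which is the true value.

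**Step 6: other slopes.** A separate calculation held the total Week 52 SD at 0.85, with baseline SD 0.6 to 0.8.

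- Slopes −0.25 to −0.40: SE 0.4% to 1.4% larger.
- Slopes −0.10 to −0.50: 3% to 10% larger.
- Slopes −0.10 to −0.60: 5% to 18% larger.

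In all three, planned-model power stays above 90%. A small simulation (250 trials per setting), run with and without about 6% dropout missing at random, gave mean estimates for the two models within 0.007 of each other.

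**Step 7: power by reading of 0.85.** Over the grid of Step 4, planned-model power is 89.7% to 93.9% if 0.85 is unadjusted, and 85.9% to 90.1% if it is already adjusted.

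**The case against.** The case for leaving the model alone is substantial. It is a legitimate prespecified choice, stated alike in protocol and SAP, and it gives an unbiased comparison. Every quantity that drives the loss is assumed. A material loss needs a growing slope and a rising residual variance together. If growth is mild (−0.25 to −0.40), the loss is only about 0% to 1.6% in SE over the same baseline SDs, correlations and residual profiles, and under 1 point of power even if 0.85 is adjusted. Setting values after rescue to missing may also remove some of the worst late values and so limit the rise in variance; the main calculations used complete data and do not model this. Finally, the plain reading of protocol 7.5 is an unadjusted SD, and then the stated 90% is not in danger.

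All of this stands as a limit on the size of the point, and it is why the point is optional. It does not remove the point. The mild-growth result lies inside the stated 0% to 8.3% range. The trade is also uneven: the term costs 0.1% to 0.3% in SE when it is not needed and can recover several per cent when it is.

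A further objection is that the other HbA1c models cannot be seen, because parts of the SAP are redacted. However, SAP 7.4.1 refers to other MMRM analyses, and Table 6.3:1 lists further analyses of the primary endpoint, so consistency across them is a reasonable request.

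**Conclusion.** The point holds as an optional improvement. The planned model is valid, and the sample size reproduces. Relative to visit-specific slopes, the single slope can enlarge the Week 52 SE by 0% to 8.3% on the main assumed grid. It costs close to nothing if slopes are equal, and about 1% or less in most settings with flat residual variance. Steeper assumed slopes give more, up to 18%. In a deliberately extreme case (slopes 0 to −0.7, compound symmetry) planned power drops to about 86–89% even with 0.85 as a raw SD.

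On the main grid, 90% power is essentially kept if 0.85 is unadjusted and can fall by up to about 4 points if it is already adjusted. Confidence in the direction is good. Confidence in the size is only medium, because the slopes, variances and correlations are not in the documents.

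**What to change.** Before unblinding, add a baseline-HbA1c-by-visit term to the primary model in SAP 7.4.1, and to the other HbA1c analyses that use the same MMRM. Keep the other covariates, the covariance rule, the degrees of freedom and the Week 52 contrast as they are. Because protocol 7.2.2 fixes the model, enter the change in SAP Section 4, whose list opens "Descriptions in the CTP related to statistical analysis will be changed as follows".

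The cost is one term with four extra parameters, the SAP wording and the Section 4 entry. No new data are needed. If the slopes are in fact equal, the Week 52 SE is about 0.2% larger. The change should be fixed before unblinding so that it cannot be read as a choice driven by the results.

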3.3.1 Main diagnosis for trial entry

The trial will be performed in the elderly Japanese patients with T2DM. Two populations will be recruited; patients who are treatment naïve and have insufficient glycaemic control, and patients who have insufficient glycaemic control despite of stable antidiabetic treatment for 12 weeks (any thiazolidinedione therapy has to be unchanged for 18 weeks).

Please refer to Section [8.3.1](#) (Source Documents) for the documentation requirements pertaining to the in- and exclusion criteria.

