3.3.2 Inclusion criteria

1. Japanese¹ patients with diagnosis of T2DM prior to informed consent

¹ Japanese is defined as patient has parents who are Japanese.

Proprietary confidential information © 2020 Boehringer Ingelheim International GmbH or one or more of its affiliated companies

2. HbA1c $\geq 7.0\%$ and $\leq 10.0\%$ for patients at Visit 1 (screening)
If the patient is on treatment with oral antidiabetic drug(s) potentially associated with severe hypoglycaemia (e.g., sulfonylurea or glinides), the following HbA1c value is used as criterion
 - 1) HbA1c $\geq 7.5\%$ and $\leq 10.0\%$ for age ≥ 65 and < 75
 - 2) HbA1c $\geq 8.0\%$ and $\leq 10.0\%$ for age ≥ 75
3. Patients on diet and exercise regimen who are drug-naïve² or on treatment with any oral antidiabetic drug (OAD) other than Glucagon-Like Peptide-1 (GLP-1) agonists and SGLT-2 inhibitor. Antidiabetic therapy has to be unchanged for 12 weeks prior to randomisation (any thiazolidinedione therapy has to be unchanged for at least 18 weeks prior to informed consent).
4. Age ≥ 65 years at informed consent
5. BMI $\geq 22 \text{ kg/m}^2$ at Visit 1 (screening)
6. Male or post-menopausal³ female patients
7. Patient signed and dated written informed consent in accordance with ICH-GCP and local legislation prior to admission to the trial

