7.1 NULL AND ALTERNATIVE HYPOTHESES

The effect of empagliflozin 10 mg will be tested against placebo at a two-sided $\alpha = 0.05$ level of significance.

H0: Mean change from baseline in HbA1c after 52 weeks of treatment with empagliflozin 10 mg = mean change from baseline in HbA1c after 52 weeks of treatment with placebo

against

H1: Mean change from baseline in HbA1c after 52 weeks of treatment with empagliflozin 10 mg \neq mean change from baseline in HbA1c after 52 weeks of treatment with placebo.

The primary endpoint will use HbA1c units of %.

Secondary endpoints and further endpoints will be evaluated in an exploratory manner.

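### The primary MMRM omits baseline background antidiabetic therapy although drug-naive and treated patients are mixed by design: a valid analysis that forgoes a small, cheap precision gain

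*SAP*

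**What the plan says.** Protocol 3.3.1 states that "Two populations will be recruited": treatment-naive patients, and patients inadequately controlled on stable antidiabetic therapy. Protocol 3.3.2 sets a general HbA1c entry floor of 7.0%. It raises the floor for some treated patients ("If the patient is on treatment with oral antidiabetic drug(s) potentially associated with severe hypoglycaemia", with sulfonylurea and glinides as examples) to 7.5% at ages 65 to under 75 and to 8.0% from age 75.

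Randomisation is stratified by screening HbA1c and age only (Protocol 4.1.3 and 7.4). Protocol 7.2.2 specifies "fixed classification effects for treatment, gender, baseline renal function, visit and visit-by-treatment interaction", plus baseline HbA1c and age as linear covariates. SAP 7.4.1 gives the same covariates: "baseline HbA1c + age + baseline renal function + sex + visit by treatment interaction + random error". The two documents agree, and neither model contains background therapy.

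The information is available. SAP 7.2 summarises concomitant therapies at baseline, and SAP 7.8.1.3 already groups hypoglycaemic events by background medication.

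**The concern.** Background therapy defines the two populations, yet neither the randomisation nor the visible primary model uses it. The plan does adjust for sex and renal function, which are not strata either, and the visible text gives no reason for stopping there.

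Background drugs are meant to stay fixed for the whole trial (Protocol 4.2.1). A naive placebo patient therefore has no glucose-lowering drug unless rescued, while a treated one continues theirs. A difference in 52-week HbA1c change between the groups is plausible, although the documents do not quantify it. Baseline HbA1c and age stand in for the factor only in part: above the entry floors, patients with the same HbA1c can be naive, on other oral drugs, or on a sulfonylurea or glinide.

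At stake is the width of the primary confidence interval and the absence of a pre-specified response to a visible imbalance. A term added only after an imbalance has been seen would be post hoc and less credible.

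There is a secondary, conditional reason. Values after rescue are set to missing, and starting rescue is at the investigator's discretion. If that decision depends on background therapy beyond the observed HbA1c, including the factor makes the missing-at-random assumption of the MMRM more credible. The documents do not show that it does.

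**Working it through.** **1. The plan's own figure.** Protocol 7.5 assumes a difference that "can be assumed to be 0.5% with a standard deviation of 0.85" (percentage points), with 1:1 allocation and a two-sided 5% test.
- Normal approximation: n = 2 × (1.960 + 1.282)² × 0.85² / 0.5² = 60.7, so 61 per arm.
- Noncentral t: power is 89.7% at 61 per arm and 90.1% at 62. The planned 62 is reproduced.
- Loss of 3% from the FAS: 62 / 0.97 = 63.9, so 64 per arm, as stated.
- Standard error without the term: 0.85 × √(2/62) = 0.153.

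**2. Gain from adjustment.** Two inputs are assumed because the documents give neither: p, the naive share (0.15 to 0.5), and d, the naive-versus-treated difference in week-52 change that the existing covariates leave unexplained (0.2 to 0.5 points). Then R² = p(1−p)d² / 0.85², and the adjusted SE is the original multiplied by √(1−R²). Power is by noncentral t at 62 per arm, with one degree of freedom fewer.

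| p | d | R² | SE reduction | Power |
|---|---|---|---|---|
| none | none | 0 | 0 | 90.1% |
| 0.15 | 0.2 | 0.0051/0.7225 = 0.7% | 0.4% | 90.3% |
| 0.3 | 0.3 | 0.0189/0.7225 = 2.6% | 1.3% | 90.9% |
| 0.5 | 0.5 | 0.0625/0.7225 = 8.7% | 4.4% | 92.5% |

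**3. Chance imbalance.** The 95% limit for the between-arm difference in naive share is 1.96 × √(2p(1−p)/62), which is 12.6 percentage points at p = 0.15 and 17.6 at p = 0.5. Multiplied by d, it shifts the unadjusted estimate by 0.126 × 0.2 = 0.025 to 0.176 × 0.5 = 0.088 points. That is 0.16 to 0.58 of one SE, or 5-18% of the assumed 0.5 effect. These are limits, not expected values.

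**4. Validity without the term.** A complete-data simulation of the week-52 comparison (20,000 runs per setting; p and d of 0.3/0.3, 0.3/0.5 and 0.5/0.5) gave a mean estimate of about −0.50 with or without the term when the true effect was −0.5. Type I error without the term was 4.9-5.1%. The empirical SE was 0.151-0.153 without the term and 0.145-0.152 with it. This was a two-arm linear model, not the full MMRM.

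**5. Form of the term.** Suppose the naive-versus-treated difference grows linearly to d at week 52. At weeks 4, 12, 24, 36 and 52 it is then 4/52, 12/52, 24/52, 36/52 and 52/52 of d. A single coefficient common to all visits estimates a weighted average of these. With equal SDs and equal correlations across visits, that average is 128/260 = 0.49 of d. If the SD rises over visits (0.4 to 0.85 was assumed), the recovered share runs from below zero to about a third, depending on the correlations. A main effect alone would therefore miss much of the week-52 difference, and the gains in step 2 need a visit-specific term.

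**The case against.** The strongest reply is that this is a modelling preference. Protocol and SAP agree on a pre-specified model that already contains both stratification variables as continuous covariates. Leaving out one further prognostic factor under randomisation is legitimate. This stands: a reader might infer a biased estimate, an inflated type I error or a protocol-SAP conflict, and the documents and step 4 support none of these. Nor is the trial underpowered for this reason, since the planned 90% rests on the SD of 0.85 and reproduces without the term.

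A second reply is that the mechanism is weak. The endpoint is change from baseline, and antidiabetic therapy must be stable for 12 weeks before randomisation and unchanged afterwards, so much of a background drug's effect is already in baseline HbA1c. The entry floors also tie sulfonylurea or glinide use to HbA1c and age, both modelled. This stands in part. It rules out the stronger reading that nothing corrects an imbalance: whatever runs through HbA1c, age, sex or renal function is adjusted. It is also why d must be read as a residual difference. It does not show that d is zero.

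Third, the figure of up to 18% of the effect is a 95%-limit imbalance under the most favourable assumptions. It is ordinary sampling error, which the confidence interval already covers. This also stands.

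Finally, part of SAP Section 4 is redacted and SAP 6.4, which defines the categories, is not public. SAP Table 6.3: 1 plans subgroup analyses of the primary endpoint. A background-therapy analysis may exist among these, so its absence cannot be claimed. The visible primary model nevertheless lacks the term.

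**Conclusion.** The point holds as a modest efficiency improvement, not as an error. The primary model leaves out a recorded baseline factor that the protocol uses to define its population, and the randomisation does not balance it. The consequence is a slightly wider interval than necessary and no adjustment for the residual part of a chance imbalance.

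Under the assumed ranges, power would rise by 0.2 to 2.4 points, and by under 1 point in the mid case. These figures depend entirely on a naive share and a residual prognostic difference that the documents do not supply. They also rest on a single week-52 comparison, which the MMRM would match only if the term is allowed to vary by visit.

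**What to change.** Before unblinding, add baseline background antidiabetic therapy (none versus any oral antidiabetic drug) to the MMRM in SAP 7.4.1 as a fixed classification effect together with its interaction with visit, and record this in SAP Section 4 as a change from Protocol 7.2.2. The interaction is needed for the week-52 contrast to be adjusted for the week-52 difference.

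A third level for sulfonylurea or glinide users is acceptable only under a fixed numeric pooling rule stated in advance, for example merging the two treated levels if either has fewer than 10 patients across both arms. If the sponsor prefers to keep the primary model as it is, the same model can be pre-specified as a sensitivity analysis.

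The cost is SAP wording and a few degrees of freedom: with five post-baseline visits, the two-level factor adds 1 + 4 = 5 mean parameters. No new data are needed. If an unpublished SAP section already covers background therapy, its categories should match those used here.

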5. ASSESSMENTS

5.1 ASSESSMENT OF EFFICACY

5.1.1 HbA1c

HbA1c is considered appropriate to evaluate the efficacy as primary endpoint because HbA1c is an internationally accepted endpoint of stable glycaemic control.

Blood samples for the determination of HbA1c at the central laboratory will be taken at all the visits except Visit 2, the blood sample can be taken at any time during the visit. For the determination of HbA1c, 3 mL of blood will be collected. The samples will be analysed at a central laboratory having a National Glycohaemoglobin Standardisation Program (NGSP) Level I certificate. Further details about sample handling, shipment, and assay procedures can be found in the ISF (Lab manual).

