6.3 SUBJECT SETS ANALYSED

The following analysis sets will be defined for this trial.

SCR - Screened patients set

All patients screened for the trial, with informed consent given and who completed at least one screening procedure at Visit 1.

RS - Randomised set

All patients from the screened set who were randomised to trial medication, regardless of whether any trial medication was taken.

TS – Treated set

All patients randomized and treated with at least one dose of trial medication. The TS is the basis for safety analyses.

FAS - Full analysis set

All patients randomised, treated with at least one dose of trial medication, and with a baseline and at least one on-treatment HbA1c value. The FAS is the basis for the ITT analysis.

PPS - Per-protocol set

All patients in the FAS without iPD leading to exclusion.

In [Table 6.3: 1](#) the data sets which are to be used for each category class of endpoint are illustrated. Note that the number of patients with available data for an endpoint may differ. For details, see [Section 6.6](#) “Handling of missing data and outliers”.

Table 6.3: 1 Summary of which data sets will be used for which class of endpoints

Class of endpoint	TS	FAS	PPS
Primary endpoint		OC, OC-IR, LOCF	OC
Subgroup analyses of primary endpoint		OC	
Further endpoints (binary)		NCF	
Further endpoints (continuous)		OC, OR#	
Safety endpoints	OR, OC-IR [^]		

#OR results will only be presented for time to first rescue medication and number of patients with rescue.

[^]OC-IR will be used for secondary endpoints and laboratory measurements.

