7.8.5 Others

Time curve analysis

Descriptive statistics will be presented in tables for creatinine, eGFR, haematocrit, haemoglobin and weight over time by treatment. Presented values will be used to create plots of the parameters over time.

In addition, tables of descriptive statistics for creatinine, eGFR values will also be presented for age subgroups.

Secondary endpoints analyses

Secondary endpoints in this trial only provide one post-baseline assessment (no repeated measurements). ANCOVA will be performed to compare the change from baseline in each of the continuous secondary endpoints at week 52 on the TS (OC-IR).

The statistical model will be: Change from baseline in secondary endpoint after 52 weeks = baseline secondary endpoint + age + sex + treatment + BMI + baseline HbA1c + random error.

In addition, descriptive statistics will be provided by visit including actual values and change from baseline values in the abovementioned secondary endpoints at Week 52. Descriptive statistics will also be presented with boxplots in each group both at baseline and at Week 52.

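### If the unstructured MMRM fit fails (unlikely), every listed fallback imposes one variance on all visits, so the Week 52 standard error can be wrong in either direction

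*SAP*

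**What the plan says.** SAP 7.4.1 fits the change in HbA1c at each on-treatment visit by REML with an unstructured within-patient covariance. The only alternative is a convergence fallback, given in both documents. SAP 7.4.1: "the following structures will be tested: compound symmetry, variance components and Toeplitz". Protocol 7.2.2: "If this unstructured covariance structure fails to converge, the following structures will be tested: compound symmetry, variance components and Toeplitz". AIC then selects among those three.

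The result is read at one visit: "The treatment effect will be estimated on the basis of the least square mean treatment difference at week 52". Degrees of freedom are Kenward-Roger and the test is two-sided at 0.05. HbA1c is measured repeatedly (Protocol 5.1.1: "HbA1c at the central laboratory will be taken at all the visits except Visit 2"), and SAP Table 6.7: 2 gives five post-baseline visits: Weeks 4, 12, 24, 36 and 52.

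The fallback is not confined to the primary analysis: "This rule will also be used for other MMRM analyses unless otherwise stated". The visible text names no structure with visit-specific variances, no step to retry the unstructured fit, and no robust standard error.

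**The concern.** The unstructured model lets the variance of the HbA1c change differ by visit. Compound symmetry, variance components and Toeplitz, as normally defined, each have a single diagonal variance. All three candidates share that restriction, so AIC cannot select a way out of it. Kenward-Roger starts from the fitted covariance, so it does not repair it either.

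This matters because the treatment effect is a single-visit contrast. Under a one-variance structure the Week 52 standard error reflects an average over visits rather than the Week 52 variance. The only confirmatory test and its 95% confidence interval come from that contrast. If the fallback were used, a variance rising to Week 52 would make the interval too narrow, and a falling one would cost power.

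**Working it through.** **Inputs from the documents.** Difference and SD for the 52-week change: "can be assumed to be 0.5% with a standard deviation of 0.85" (Protocol 7.5, in % HbA1c). 62 evaluable per arm, 3% loss, 64 randomised per arm, 90% power, two-sided 5%. Five post-baseline visits.

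**The plan's own figure.** A two-sample t-test with difference 0.5 and SD 0.85 has power 0.897 at 61 per arm and 0.901 at 62. Then 62 / 0.97 = 63.9, so 64. The stated sample size reproduces and is not affected by this point.

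**Trigger.** Unstructured covariance for 5 visits has 5 x 6 / 2 = 15 parameters, for about 2 x 62 = 124 patients. In 2,500 simulated fits (an optimiser other than SAS) it converged every time. The upper 95% bound on failure in those runs is 3 / 2,500 = 0.12%.

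**Standard error under the present fallbacks.** True Week 52 SE with complete data: 0.85 x sqrt(2/62) = 0.153. For compound symmetry and variance components:

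- SE ratio (model / true) = sqrt(mean visit variance / Week 52 variance)
- type I error = 2 x (1 - Phi(1.96 x ratio))

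The SDs before Week 52 are assumptions. Worked example, steep rise: mean variance = (0.1600 + 0.3600 + 0.5184 + 0.6400 + 0.7225) / 5 = 0.4802; ratio = sqrt(0.4802 / 0.7225) = 0.815; type I error 11.0%.

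For Toeplitz, the large-sample fit was found by minimising log|V| + trace(V^-1 S), where S is the true covariance. Seven assumed correlation patterns were used: AR(1) 0.6, 0.8 and 0.9 per visit; 0.8 per 12 weeks at the actual visit weeks; compound symmetry 0.5 and 0.7; and a shared 0.5 plus AR(1) 0.6.

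| Assumed SD at Weeks 4/12/24/36/52 | SE ratio, CS and VC | Model SE | Type I, CS and VC | Type I, Toeplitz |
|---|---|---|---|---|
| 0.40/0.60/0.72/0.80/0.85 | 0.815 | 0.124 | 11.0% | 11.1% to 12.1% |
| 0.60/0.70/0.78/0.82/0.85 | 0.889 | 0.136 | 8.2% | 8.2% to 8.7% |
| 0.75/0.78/0.80/0.83/0.85 | 0.944 | 0.144 | 6.4% | 6.4% |
| 0.85 throughout | 1.000 | 0.153 | 5.0% | 5.0% |
| 0.95/0.95/0.92/0.88/0.85 | 1.072 | 0.164 | 3.6% | 3.6% to 3.7% |

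In the falling case, power (normal approximation) drops from Phi(0.5/0.1527 - 1.96) = 90.6% to Phi(0.5/0.1527 - 1.96 x 1.072) = 88.0%.

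**Check with dropout.** REML fits of the three structures with AIC choice were simulated 600 times per scenario (62 per arm, 12% random dropout assumed, no covariates). AIC chose Toeplitz every time. Rejection under the null was 5.8% with flat variance, 11.7% with SDs 0.50/0.65/0.75/0.80/0.85, and 14.5% with SDs 0.35/0.55/0.70/0.80/0.85 (Monte Carlo SE about 1 to 1.5 points).

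**Heterogeneous alternatives.** The same complete-data criterion was applied to the five SD patterns and seven correlation patterns, plus three patterns in which adjacent-visit correlation strengthens over time (0.70/0.75/0.80/0.85, 0.60/0.70/0.80/0.85 and 0.50/0.65/0.80/0.85, with products for longer lags). For these structures the SE ratio does not depend on the SD pattern.

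| Structure | Covariance parameters | Type I, first seven patterns | Type I, strengthening correlation |
|---|---|---|---|
| Heterogeneous compound symmetry | 6 | 3.7% to 5.0% | 4.8% to 5.3% |
| Heterogeneous AR(1) | 6 | 3.8% to 5.0% | 6.6% to 7.8% |
| Heterogeneous Toeplitz | 9 | 3.8% to 5.0% | 6.6% to 7.9% |

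**Unconditional size.** Worst complete-data excess 12.1 - 5.0 = 7.1 points; 7.1 x 0.0012 = 0.009 percentage points. With the 14.5% simulation figure, 9.5 x 0.0012 = 0.011.

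**The case against.** The strongest objection is immateriality. Unstructured covariance comes first, and the fallback and its selection rule are prespecified and identical in both documents. The event that triggers them should hardly ever occur. This stands, and it is why the point is minor.

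Second, the sizes rest on assumptions: four of the five SDs in each pattern, and all the correlations. The calculations also omit covariates and post-rescue censoring. This stands too: the algebra shows that an error arises whenever variance is not flat, but not which way it goes.

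Third, changing to heterogeneous structures is not automatically safer. If correlation strengthens over time, heterogeneous Toeplitz and AR(1) are anti-conservative even when variance is flat, where the present list gives 5.0%. Under the steep rise they still improve on homogeneous Toeplitz (6.6% to 7.9% against about 11.6%). This objection is right and governs the order proposed in the fix.

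A reader might infer that the planned primary test has an inflated type I error. The documents do not support that: the fallback is conditional, and no SD is given for any visit before Week 52. Nor does the point reach the secondary endpoints, which are analysed by ANCOVA (SAP 7.8.5: "Secondary endpoints in this trial only provide one post-baseline assessment (no repeated measurements"). SAP Table 6.3: 1 lists "Subgroup analyses of primary endpoint" along with per-protocol, OC-IR and LOCF analyses of HbA1c. The visible text does not say which of these use MMRM. Any that do, in fewer patients, would have the same 15 parameters to estimate and so a less remote chance of failure.

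**Conclusion.** The concern holds conditionally. If the unstructured fit fails, every listed fallback ties the Week 52 standard error to the average visit variance, and neither AIC nor Kenward-Roger corrects this. Given the fallback, type I error is about 3.6% to 12% across the assumed complete-data patterns, and 5.0% if variance is flat; one simulation with dropout and a steeper assumed rise reached 14.5%. Unconditionally the effect is about 0.01 percentage points or less, on the simulated bound for non-convergence, which may not carry over exactly to SAS and the real data.

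The conclusion assumes the standard one-variance forms of the three structures. It also rests on the visible text: three entries in SAP Section 4 are blacked out and SAP Section 10 is not visible. Optional improvement; no change to the primary model or sample size is called for.

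**What to change.** Before unblinding, replace the fallback sentence in SAP 7.4.1 with an ordered rule:

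1. Retry the unstructured fit with other starting values or optimiser settings.
2. If it still fails, use a structure with visit-specific variances: heterogeneous compound symmetry first, then heterogeneous AR(1) or heterogeneous Toeplitz, in an order fixed in the SAP. Keep Kenward-Roger.
3. As a last resort, use a one-variance structure with an empirical (sandwich) standard error and a named, suitable degrees-of-freedom method.

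Record the departure from Protocol 7.2.2 in SAP Section 4.

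The cost is a wording change, one entry in Section 4 and a few lines of code. The statistical price is more covariance parameters (6 or 9, against 1 to 5 now) and loss of the AIC choice. Any structured correlation can also be wrong in either direction. Heterogeneous compound symmetry goes first because it stayed closest to 5% when correlation strengthened over time, but it is not guaranteed: it ranged from 3.7% to 5.3% in the settings checked. Making the change now avoids an ad hoc choice after a failed fit on unblinded data.
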